9.4 INSPECTIONS

Site visits will be conducted by the Sponsor or an authorized representative for inspection of study data, patients' medical records, and eCRFs. The investigator will permit national and local health authorities; Sponsor monitors, representatives, and collaborators; and the IRBs/ECs to inspect facilities and records relevant to this study.

9.5 ADMINISTRATIVE STRUCTURE

This trial will be sponsored and managed by F. Hoffmann-La Roche Ltd. The Sponsor will provide clinical operations management, data management, and medical monitoring.

Approximately 50 patients will be enrolled in this study.

Patients can be identified by means of one of the two following enrollment pathways:

- The Precision Enrollment approach offered by FMI. When non-lung cancer samples are determined by FMI central testing to be positive for ALK, an FMI medical oncologist will contact the ordering physician (local oncologist) and provide information about the trial. If this is of interest to both the physician and the patient, enrollment procedures will begin
- Patients with ALK-positive NGS test results obtained outside FMI's Precision Enrollment may be identified and the local ALK NGS test report will be made available (see Section 4.6.6) and will be assessed by the investigator for eligibility. The study team and Medical Monitor are to be consulted. If ALK positivity is not accepted per the criteria, prospective FMI testing is required and the patient may be enrolled if assessed to be ALK-positive by FMI.

For sample requirements, see Section 4.6.6 and Appendix 2, Table 3.

For eligible and enrolled patients, the tumor tissue sample must be submitted (see Section 4.6.6 and Appendix 2, Table 3) for retrospective analysis by FMI using the F1CDx assay.

A decentralized, home-based approach will be adopted that minimizes the need of on-site visits for patients, thus making clinical trials more accessible to patients regardless of location. Central facilities will be used for certain study assessments throughout the study (e.g., specified laboratory tests, biomarker and PK analyses), as

Alectinib—F. Hoffmann-La Roche Ltd

specified in Section 4.6. Accredited local laboratories may be used for patient safety follow-up; local laboratory ranges will be collected.

BICR of tumor assessments will be conducted to determine the secondary endpoints of confirmed ORR, DOR, PFS, CNS ORR, and CNS DOR, all according to RECIST v1.1. In addition, BICR of tumor assessments of primary CNS tumors will be conducted according to the RANO criteria.

The independent review of MRI and CT scans will not be used to determine either eligibility or patient treatment. All treatment decisions will be made by the investigator using local assessments.

An IMC will monitor patient safety throughout the study, focusing on death cases and interim futility analysis.

9.6 DISSEMINATION OF DATA AND PROTECTION OF TRADE SECRETS

Regardless of the outcome of a trial, the Sponsor is dedicated to openly providing information on the trial to health care professionals and to the public, at scientific congresses, in clinical trial registries, and in peer-reviewed journals. The Sponsor will comply with all requirements for publication of study results. Study data may be shared with others who are not participating in this study (see Section 8.4 for details), and redacted Clinical Study Reports and other summary reports will be made available upon request. For more information, refer to the Roche Global Policy on Sharing of Clinical Study Information at the following website:

www.roche.com/roche_global_policy_on_sharing_of_clinical_study_information.pdf

The results of this study may be published or presented at scientific congresses. For all clinical trials in patients involving an IMP for which a marketing authorization application has been filed or approved in any country, the Sponsor aims to submit a journal manuscript reporting primary clinical trial results within 6 months after the availability of the respective Clinical Study Report. In addition, for all clinical trials in patients involving an IMP for which a marketing authorization application has been filed or approved in any country, the Sponsor aims to publish results from analyses of additional endpoints and exploratory data that are clinically meaningful and statistically sound.

The investigator must agree to submit all manuscripts or abstracts to the Sponsor prior to submission for publication or presentation. This allows the Sponsor to protect proprietary information and to provide comments based on information from other studies that may not yet be available to the investigator.

In accordance with standard editorial and ethical practice, the Sponsor will generally support publication of multicenter trials only in their entirety and not as individual center data. In this case, a coordinating investigator will be designated by mutual agreement.

Alectinib—F. Hoffmann-La Roche Ltd
Authorship will be determined by mutual agreement and in line with International Committee of Medical Journal Editors authorship requirements. Any formal publication of the study in which contribution of Sponsor personnel exceeded that of conventional monitoring will be considered as a joint publication by the investigator and the appropriate Sponsor personnel.

Any inventions and resulting patents, improvements, and/or know-how originating from the use of data from this study will become and remain the exclusive and unburdened property of the Sponsor, except where agreed otherwise.

Appendix 1 Schedule of Activities

	Screening		Treatment Per	iod	Treatment		
Assessment	Days -28 to -1	Baseline (Week 1)	Q2W (±3 days) for the First 12 Weeks ^h	Q4W thereafter until PD, Death, or Withdrawal from Study ^a (±3 days)	Discontinuation Visit (28 days after Final Dose of Study Drug [±5 days])	Off-Tx Visits ⁵	Long- Term Follow- Up °
Informed consent	х						
Demographic data	х						
Medical history, baseline conditions	x						
ECOG Performance Status	х	х		x	х		
Vital signs	х	х		x	х		
Weight	х	х		x	х		
Height	х						
Physical examination ^d	х	х		x	х		
ECG	х	х		As clinically indicated	х		
Coagulation ^e	х	x		As clinically indicated	х		
Hematology ^f	х	х		x	х		
Chemistry ^g	x	x		x	x		
Urinalysis, dipstick	x	x		x	x		

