Alectinib—F. Hoffmann-La Roche Ltd 50/Protocol BO41929, Version 4 database (RAVE) to allow the Sponsor's study team to perform data management and medical review, and generate queries accordingly. Queries will be answered by the investigator or designee. Details related to source data, data capture, and cleaning can be found in the country-specific operations manual.

On-Study Visits: Assessments and Procedures

Study visits will be performed at patients' homes according to the schedule of activities as outlined in Appendix 1.

All necessary study supplies, including the study drug, will be shipped by secure courier to the patient's home (or, alternatively, see Section 4.4.3) ahead of the scheduled study visits. Return labels will be included so patients can return supplies to vendor once study participation is completed or upon discontinuation.

The CRC will schedule visits taking into consideration the patients' availability and the allowed visit windows and will notify the investigator and mHCP, as applicable. The coordinating responsible will set up the appointment for the investigator to perform the telemedicine remote visits and remind the patient of upcoming visits and procedures that will take place during the visit. In addition, the coordinating responsible will provide remote coordination and technical assistance during all visits. The patient will be provided with a mobile device for the duration of the study to facilitate interactions with the investigator, the mHCP, and the coordinating responsible. See the country-specific operations manual for more details.

For tests that cannot be performed at home (such as scans for tumor assessments), arrangements will be made for patients to visit a local facility that can perform the required tests.

Unscheduled visits will also be performed at patients' homes if possible. However, it may be necessary that patients visit a local laboratory/specialist or the local oncologist for safety reasons, as needed. Records generated from these visits will be obtained and sent to investigator or uploaded into the relevant data capture system for documentation and the investigator's review.

For details on procedures and assessments to be performed at each visit, see the schedule of activities in Appendix 1.

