4.7 TREATMENT, PATIENT, AND STUDY DISCONTINUATION

Patients will continue on study treatment until disease progression, discontinuation, withdrawal of consent, or death, whichever occurs first.

Treatment beyond radiological progression is possible in the event of isolated lesion progression if, in the investigator's opinion, there is evidence of ongoing clinical benefit.

In the event of a patient's voluntary withdrawal of consent, the investigator will make a reasonable effort to document the reported reason for consent withdrawal in the eCRF. All efforts will be made to complete the assessments prior to study withdrawal, as detailed in the protocol.

For patients whose status is unclear because they fail to communicate with the study personnel without confirming discontinuation or withdrawal, study personnel will show due diligence by documenting all actions taken to contact the patient (e.g., dates of telephone calls, registered letters, etc.).

Patients will not be considered as lost to follow-up until due diligence has been completed or until the end of the study.

4.7.1 Study Treatment Discontinuation

Patients must permanently discontinue study treatment if they experience any of the following:

- Any medical condition that the investigator or Sponsor determines may jeopardize the patient's safety if he or she continues to receive study treatment
- Investigator or Sponsor determination that treatment discontinuation is in the best interest of the patient
- Pregnancy

Alectinib—F. Hoffmann-La Roche Ltd 65/Protocol BO41929, Version 4

- Use of an anti-cancer therapy not required per protocol
- Symptomatic deterioration attributed to disease progression
- Any event that meets stopping criteria defined in Section 5.1.2

The primary reason for study treatment discontinuation should be documented on the appropriate eCRF. Patients who discontinue study treatment prematurely will not be replaced. Patients with ALK-fusion tumors who are enrolled in the study and do not receive any dose of study treatment will be replaced.

The mHCP will perform a treatment discontinuation visit 28 days after the final dose of alectinib for safety assessments as described in the schedule of activities (see Appendix 1).

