5.3.1 Adverse Event Reporting Period

Investigators will seek information on adverse events at each patient contact. All adverse events, whether communicated by the patient or noted by study personnel, will be recorded in the patient's medical record and on the Adverse Event eCRF by the investigator.

After informed consent has been obtained but prior to initiation of study drug, only serious adverse events caused by a protocol-mandated intervention (e.g., invasive procedures such as biopsies, discontinuation of medications) should be reported (see Section 5.4.2 for instructions for reporting serious adverse events).

After initiation of study drug, all adverse events will be reported until 28 days after the final dose of study drug.

Instructions for reporting adverse events that occur after the adverse event reporting period are provided in Section 5.6.

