5.4.3.1 Pregnancies in Female Patients

Female patients of childbearing potential will be instructed through the Informed Consent Form to immediately inform the investigator if they become pregnant during the study or within 90 days after the final dose of study drug. A paper Clinical Trial Pregnancy Reporting Form should be completed and submitted to the Sponsor or its designee immediately (i.e., no more than 24 hours after learning of the pregnancy), either by faxing or by scanning and emailing the form using the fax number or e-mail address provided to investigators. Pregnancy should not be recorded on the Adverse Event eCRF. The investigator should discontinue study drug and counsel the patient, discussing the risks of the pregnancy and the possible effects on the fetus. Monitoring of the patient should continue until conclusion of the pregnancy. Any serious adverse events associated with the pregnancy (e.g., an event in the fetus, an event in the mother during or after the pregnancy, or a congenital anomaly/birth defect in the child) should be reported on the Adverse Event eCRF. In addition, the investigator will submit a Clinical Trial Pregnancy Reporting Form when updated information on the course and outcome of the pregnancy becomes available.

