Appendix 1: Schedule of Activities

CPK = creatine phosphokinase; CT = computed tomography (scan); eCRF = electronic Case Report Form; ECOG = Eastern Cooperative Oncology Group; FFPE = formalin fixed, paraffin embedded; FMI = Foundation Medicine, Inc.; GGT = gamma-glutamyl transferase; MRI = magnetic resonance imaging; NA = not applicable; NGS = next-generation sequencing; PD = progressive disease; PK = pharmacokinetic; PRO = patient-reported outcome; Q2W = every 2 weeks; Q4W = every 4 weeks; Q8W = every 8 weeks; RBR = Research Biosample Repository; SFU = survival follow-up; Tx = treatment; WES = whole exome sequencing; WGS = whole genome sequencing.

Notes: Results of laboratory tests and ECG performed within 3 days before first dose of study drug can be used as baseline assessments.

- ^a Treatment beyond radiological progression is possible in the event of isolated lesion progression if in the investigator's opinion there is evidence of ongoing clinical benefit. For patient receiving study drug beyond radiological progression, scheduled visits (including disease assessments) will continued to be performed until treatment discontinuation.
- ^b For patients who discontinue study treatment prematurely for reasons other than disease progression, tumor assessments should continue until progression.
- c Required follow-up information (e.g., survival status and information on further cancer therapies and procedures [radiotherapy, surgery]) will be collected via telephone calls every 3 months (±14 days) until death, loss to follow-up, or study termination by the Sponsor. More frequent calls may be required when clinical data cut-offs are performed.
- ^d Complete physical examination (head, eyes, ears, nose, and throat, and the cardiovascular, dermatologic, musculoskeletal, respiratory, gastrointestinal, genitourinary, and neurologic systems). Baseline and post-baseline visits: limited physical examination, symptom-directed, and as clinically indicated. For patients with primary CNS tumors, a neurological examination must be performed at each tumor assessment visit and compared with the neurological examination performed at the time of the last disease assessment.
- ^e Coagulation includes PT (or INR) and aPTT (or PTT).
- ^f Includes WBC count, RBC count, hemoglobin, hematocrit, platelet count, and differential count (neutrophils, eosinophils, basophils, monocytes, lymphocytes).

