## 5.6.2 Adverse Events

Verbatim description of adverse events (AEs) will be mapped to Medical Dictionary for Regulatory Activities thesaurus terms and graded according to National Cancer Institute Common Terminology Criteria for Adverse Events (NCI CTCAE) v5.0.

After informed consent has been obtained but prior to initiation of study drug, only serious AEs caused by a protocol-mandated intervention (e.g., invasive procedures such as biopsies, discontinuation of medications) are collected.

After initiation of study drug, all adverse events will be collected until 28 days after the final dose of study drug.

After the end of the adverse event reporting period, all deaths, regardless of cause, and serious adverse events that are believed to be related to prior exposure to study drug are collected.

All AEs that occur on or after the first study drug dose (treatment-emergent AEs) will be reported. They will be summarized using descriptive statistics (i.e., frequencies and percentages) by Medical Dictionary for Regulatory Activities (MedDRA) term, appropriate MedDRA levels, and NCI CTCAE v5.0 grade, regardless of relationship to study drug as assessed by the investigator. For each patient, if multiple incidences of the same adverse events occur, the maximum severity reported will be used in the summaries.

The following treatment-emergent adverse events will be summarized separately:

- AEs
- AEs leading to withdrawal of study drug
- AEs leading to dose reduction or interruption

Alectinib—F. Hoffmann-La Roche Ltd **Statistical Analysis Plan** BO41929

- Grade 3/4 AEs, Grade 5 AEs, serious adverse events
- AEs of special interest

All deaths and causes of death will be summarized.

Subgroup analyses will be performed to evaluate the safety profile within subgroups of patients, including by sex, age (< 65 years vs.  $\geq$  65 years), region, and race.

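### The ±5-day window on the discontinuation visit lets the last scheduled adverse-event enquiry fall up to 5 days before the 28-day reporting period closes

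*Protocol*

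**What the plan says.** **Visit timing.** Appendix 1 heads the column for the last safety visit "Discontinuation Visit (28 days after Final Dose of Study Drug [±5 days"]). The body text gives no tolerance. Protocol 4.7.1 says "The mHCP will perform a treatment discontinuation visit 28 days after the final dose of alectinib for safety assessments", and Sections 3.1 (safety follow-up) and 4.5 (end of concomitant-therapy recording) also put the visit at 28 days.

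**Reporting period.** Under Protocol 5.3.1, after the first dose, "all adverse events will be reported until 28 days after the final dose of study drug". SAP 5.6.2 agrees: "After initiation of study drug, all adverse events will be collected until 28 days after the final dose of study drug". Protocol 5.4.2.2 applies the same limit to serious adverse events and adverse events of special interest.

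**What follows the visit.** In Appendix 1 the off-treatment column holds only tumor and brain imaging. The long-term follow-up column holds only subsequent therapy and survival. Footnote c gives, as examples of what the three-monthly calls collect, "survival status and information on further cancer therapies and procedures [radiotherapy, surgery"].

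**How events are elicited.** Protocol 5.3.1 adds that "Investigators will seek information on adverse events at each patient contact". Section 5.3.2 asks for consistent non-directive questioning at patient evaluation timepoints. In Section 5.3.1.1 patients agree at consent to report possible events as soon as they can.

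**Pregnancy.** The last scheduled test is at the discontinuation visit. Female patients are told to inform the investigator at once if they "become pregnant during the study or within 90 days after the final dose of study drug". Section 5.4.3.2 does the same for partners of male patients.

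**The concern.** The visit is the only post-treatment point at which Appendix 1 schedules questioning about adverse events and concomitant medications. If it takes place at the early edge of its window, the reporting period is still open but no further enquiry is scheduled within it. Events with onset in the remaining days are then found only if the patient volunteers them, another provider passes them on, or someone contacts the patient for another reason.

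The completeness of adverse-event data just after treatment would then depend on which day the visit happened to be booked. Non-serious events are the most exposed. After day 28, Section 5.6 keeps open only deaths and serious events believed to be related to study drug. The trial is home-based and safety in all dosed patients is a stated objective, so it makes sense for the last structured enquiry to cover the whole period for which the plan claims to collect events.

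**Working it through.** There is no stated figure to reproduce. The check is calendar arithmetic plus a comparison of sections.

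**Inputs**
- Visit: day 28 ± 5 after the final dose (Appendix 1)
- Adverse-event period: to day 28 (Protocol 5.3.1 and 5.4.2.2; SAP 5.6.2)
- Pregnancy reporting: to day 90 (Protocol 5.4.3.1 and 5.4.3.2)
- Long-term calls: every 3 months ± 14 days (Appendix 1, footnote c)

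**Step 1: visit range.** Earliest 28 − 5 = day 23; latest 28 + 5 = day 33.

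**Step 2: adverse-event days after the last scheduled enquiry.** Gap = max(0, 28 − visit day).

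| Visit day | Gap (days) | Share of 28 days |
|---|---|---|
| 23 | 5 | 5/28 = 17.9% |
| 28 | 0 | 0% |
| 33 | 0 | 0% |

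**Step 3: is there a later scheduled enquiry?** In Appendix 1 the adverse-event and concomitant-medication rows are marked at screening, baseline, the four-weekly visits and the discontinuation visit. The off-treatment and long-term columns are blank in both rows. Nothing scheduled for adverse events falls between an early visit and day 28.

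**Step 4: does the body text share the window?** No. Sections 3.1, 4.5 and 4.7.1 say 28 days; only Appendix 1 allows ±5. Section 4.5 ends concomitant-therapy recording at this visit and describes the visit as occurring at 28 days. Under Appendix 1 that recording could also stop on day 23.

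**Step 5: pregnancy, as a secondary matter.** Days left in the 90-day window after the last scheduled test:
- visit on day 33: 90 − 33 = 57 (63.3%)
- visit on day 28: 90 − 28 = 62 (68.9%)
- visit on day 23: 90 − 23 = 67 (74.4%)

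These figures apply to female patients who are tested, since partners of male patients are never tested. The documents do not fix the day from which the calls are counted. Taking 3 months as 91 days, the first call would fall on day 77 to 105 if counted from the final dose (91 ± 14). Counted from the visit, it would fall on day 100 (23 + 91 − 14) to day 138 (33 + 91 + 14). Section 4.7.1 starts these calls only after progression, so some patients will not be receiving them by then.

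**The case against.** The strongest reply is that nothing in the plan ends collection on day 23. The duty to report runs to day 28 whatever the visit date. Any contact on days 24 to 28 must elicit adverse events under 5.3.1, whether or not Appendix 1 has a mark. Patients have agreed to report promptly and have a study smartphone, and other providers and medical records are recognised sources (5.3.1.1). Related serious events remain reportable after day 28 (5.6). All of this stands. A reader might infer that safety collection stops before the protocol's own windows close; the documents do not support that.

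A reader might also infer that the analysis treats every patient as observed for a full 28 days, so that reported rates are biased. The text does not go that far. SAP 5.6.2 reports frequencies and percentages of events on or after first dose, with no person-time denominator. Protocol 6.5 applies a 28-day onset limit only to events judged unrelated. With a single arm, uneven visit timing cannot distort a comparison between arms.

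On pregnancy, the 90-day duty is self-report by design, instructed through the consent form. No section promises testing or scheduled questioning to day 90, so none is contradicted. The content of the calls in footnote c is introduced as an example and does not rule out a pregnancy question.

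The reply does not remove the mismatch itself. Eliciting events at each contact helps only if a contact occurs, and after an early visit none is scheduled for this purpose. Section 5.6 does not cover non-serious or unrelated events.

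**Conclusion.** The point holds as a gap in scheduled elicitation. A visit that complies with Appendix 1 can leave up to 5 of the 28 post-treatment days without a planned adverse-event enquiry. The same early visit can close concomitant-medication recording. The 5 days (17.9%) is the worst case under the window, and the gap is zero for any visit on or after day 28. How many patients would be seen early, and how many events would be missed, cannot be estimated from the documents. The finding rests on reading the blank off-treatment and long-term cells as meaning that no adverse-event enquiry is scheduled there.

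The pregnancy half is a preference, not an inconsistency. Between 57 and 67 of the 90 days have no scheduled check, but instructed self-report covers them.

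This is a low-cost improvement to safety ascertainment. It does not touch the primary endpoint, the sample size or the error rates.

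**What to change.** Reconcile Appendix 1 with the 28-day reporting period and with Sections 3.1, 4.5 and 4.7.1, so that the adverse-event and concomitant-medication enquiry at the discontinuation visit cannot precede day 28. A 0/+5-day window (day 28 to day 33) is one example. State the same window in the body text. The cost is protocol wording and slightly less flexibility in booking one visit, with no added visit or test. Visits after day 28 will turn up some events with later onset, but the current window already allows this, and onset dates settle which events fall within the period.

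Optionally, add a pregnancy question to an existing off-treatment or follow-up contact, for women of childbearing potential and for male patients about their partners. The wording should allow for the three-monthly calls beginning only after progression, so that patients who stopped treatment for other reasons are asked at an off-treatment contact. The cost is one question.
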